1.4.4.1 Pharmacokinetics of BMS-986158

BMS-986158

Interim noncompartmental PK analyses were conducted on BMS-986158 (parent) and BMT-161485 (metabolite) using samples from the monotherapy portion of the study administration of 0.75, 1.25, 2, 3, and 4.5 mg oral doses of BMS-986158 following single and multiple doses using nominal time and examining continuous and intermittent schedules (Schedules A and C, respectively).

Interim PK results indicate that BMS-986158 is moderately to rapidly absorbed (Tmax range: 0.5 to 4 hours) following single dose administration at doses of 0.75 to 4.5 mg. The exposure within the dose range examined appears to increase with increasing dose. From these multiple dosing data, a peak to trough ratio of approximately 2.4 and an accumulation index of approximately 1.97 were determined. The inter- and intra-subject variability was from low to high.

PK parameters of BMS-986158 using nominal sample times show that the overall exposure was significantly higher than predicted. This higher than predicted human exposure may have resulted from, and is consistent with a lower than anticipated clearance and increased serum protein binding in humans. Preclinical determinations of human serum protein binding indicated a 3.9% free fraction for BMS-986158. Interim data from ex vivo plasma samples collected from the 6 subjects at the 2 mg dose on this study showed mean free drug fractions of 0.1% to 0.2% with small to moderate intra- and inter-subject variability that were not concentration dependent. It is postulated that the unexpectedly low free fraction resulted in the low clearance.

The metabolite (BMT-161485) exhibited a similar terminal phase elimination as the parent drug, suggesting formation rate limited PK of BMT-161485. Plasma concentrations of metabolite were low relative to the plasma concentration of the parent drug with exposure ratios less than 30%. The metabolite has potency that is approximately 10-fold weaker than the parent drug.

Preclinical data suggests that BMS-986158 is metabolized in the liver by CYP3A4 mediated oxidation to a hydroxylated metabolite; it also undergoes glucuronidation. BMS-986158 is a substrate of CYP3A4 and an inhibitor of P-gp and transporters.

1.5 Overall Risk/Benefit Assessment

Many cancers are driven by MYC pathway and BRD4 super enhancer activation, providing a solid rationale for the trial of BET inhibitors as suppressors of BRD4 and MYC in multiple tumor types.^{9,15} Preclinical studies have linked repression of MYC and other oncogenes to tumor cell death and tumor regression in both solid tumors and hematologic cancer models, following BET inhibition.^{8,9,10},BRD4 amplification and overexpression has been correlated with adverse prognostic information.¹⁹

Sixteen other BET inhibitors have entered Phase 1/2 clinical trials, and 24 studies focused on solid tumors and hematological malignancies are recruiting patients or are completed as listed in clinicaltrials.gov.

Results from most studies have not been reported. Preliminary clinical data is available on the OTX-015/MK-8628 Phase 1 study in leukemia which shows that no DLTs were observed in 28 evaluable subjects with AML, ALL, and refractory anemia (RA) through dose level (DL) 5 (120 mg QD). At DL6 (160 mg QD), MTD was exceeded with 1 patient experiencing grade 3 diarrhea and another grade 3 fatigue and anorexia.⁴⁴ The main toxicities were non-cumulative grade 1-2 gastrointestinal events (6 patients diarrhea, 3 dysgueusia, 3 abdominal pain, 3 nausea, 1 anorexia), hyperglycemia (3 patients), coagulation factor VII decrease (6 patients) and direct bilirubin increase (3 patients) (two latter AEs asymptomatic). These toxicities were mainly observed at QD doses above 80 mg and with 40 mg BID. Clinically relevant activity was reported in 5 AML patients treated at 10, 40 and 80 mg, including one sustained CR from cycle 4 to cycle 12 (40 mg QD) and one CR with incomplete platelet recovery (CRp) from cycle 2 to cycle 5 (80 mg QD).⁴⁴ Preliminary clinical data is also available on OTX015/MK-8628 Ph 1 study in Non-Leukemic Hematologic Malignancies.⁴⁵ In this study, 37 non-leukemic patients (18 diffuse large B-cell lymphoma [DLBCL], 9 other lymphomas, 10 myeloma) were treated over 5 dose levels, 33

of whom were evaluable for DLT. No DLTs were observed through DL4 (80 mg OD). Reversible grade 4 thrombocytopenia was the DLT at DL4 BID (40 mg x2) and 120 mg OD continuous. Sixteen patients experienced Grade 3-4 thrombocytopenia and 3 patients had grade 3-4 neutropenia. Grade 3 non-hematologic toxicities were diarrhea, vomiting, hyperglycemia, and hypernatremia (1 patient each). Other toxicities were non-cumulative grade 1-2 gastrointestinal events (8 patients with diarrhea, 3 dysgueusia, 2 vomiting, 1 nausea, 1 anorexia, 1 abdominal pain), hyperglycemia (7 patients), skin rash (3 patients), asymptomatic coagulation factor VII decrease (2 patients), and direct bilirubin increase (1 patient). Clinically relevant activity was reported in 6 patients treated from 40 to 120 mg, including one CR (120 mg, 17+ weeks [wks]) and 1 PR (80 mg, 28 wks), both in DLBCL patients failing 3-4 prior therapy lines, and both with clinical benefit. Four other patients (two with DLBCL, one follicular, and one lymphoplasmacytic lymphoma) had minor tumor shrinkage with clinical benefit (40 mg, 36+ wks; 80 mg, 14 wks; 120 mg 15 wks; 120 mg, 17 wks). Similarly, a study using another BET inhibitor, CPI-0610, as monotherapy reported objective clinical responses in 5 of 36 subjects with relapsed or refractory DLBCL, specifically in T cell/histocyte-rich and activated B-cell subtypes. Of note was 1 CR and 2 PR in subjects with ABC-DLBCL, 1 PR in follicular lymphoma, and 1 PR in T-cell histocyte rich lymphoma.⁷⁷

The initial assessment of the risk of side effects of BMS-986158 in clinical trials was based on data from nonclinical toxicology studies in rats and dogs. Those studies primarily demonstrated the expected toxicity profile of BET inhibition, with most toxicity shown in the highly proliferative cell populations of the bone marrow and gastrointestinal tract. An additional toxicity observed in the rat but not dog was mammary gland atrophy in males. An additional toxicity observed in the dog but not rat was testicular degeneration. An additional toxicity finding observed in pregnant rats demonstrated embryolethality and teratogenicity. A detailed description of these toxicities is provided in Section 1.4.2 and in the Investigational Brochure. The GI and bone marrow toxicities were reversible upon discontinuation of the drug.

The nonclinical toxicity profile was used to determine the starting dose and to develop appropriate exclusion criteria, contraception measures for male and female participants, and safety monitoring for this study. In addition to frequent complete blood counts (CBCs) and chemistry (including liver enzyme) tests, because of the potential effect of immune system repression, subjects with viral infection (Human immunodeficiency virus [HIV], Hepatitis B or C) are excluded and lymphocyte numbers are monitored regularly. Immunoglobulin levels are also followed routinely to evaluate the potential need for supplementation. Although the nonclinical in vitro and in vivo assessments have not demonstrated any cardiovascular liability, electrocardiograms (ECG) are being monitored frequently. Subjects will be evaluated frequently by physical exam; their weights are being closely monitored, and they are being assessed for the development of diarrhea or other anticipated GI symptoms. Guidelines for the management of diarrhea are provided in Section 4.5.3.

As of the data cutoff date on 21-Dec-2018, preliminary clinical data from the first-in-human CA011001 monotherapy study in subjects with advanced solid tumors have demonstrated that BMS-986158 has an acceptable toxicity profile in 81 subjects treated at all dose levels in Schedule A (0.75, 1.25, 2, 3, and 4.5 mg), Schedule B (2 and 3 mg) and Schedule C (2, 3, and 4.5 mg). All

observed toxicities in the GI or hematopoietic system reversed spontaneously or upon drug withdrawal. To date, the cumulative human safety data are consistent with the non-clinical assessment of toxicity in rats and dogs and support the continued clinical exploration of BMS-986158 for the treatment of a variety of malignancies.

Although BMS-986158 does not demonstrate evidence of genotoxicity, perturbation of cellular differentiation pathways may contribute to development of cancer. Subjects are informed of the potential risk, and are carefully evaluated by the investigators throughout the study. Subjects are counseled on appropriate contraceptive measures, while on study and for at least 3 months after the last dose of BMS-986158. Additionally, subjects are informed of the potential risks to reproductive organs and the option of sperm or egg banking discussed, if appropriate.

The frequent safety assessments are utilized by the Sponsor/Medical Monitor and investigators to determine whether dose modification, additional safety measures, or termination of the study is required at any time. Thorough evaluation of the above-described safety monitoring procedures and of AEs and serious adverse events (SAEs) are reviewed on an ongoing basis by the Sponsor's Medical Monitor and Global Pharmacovigilance and Epidemiology representatives to monitor for any safety signals or trends.

As BMS-986158 is an experimental agent, it is possible that unforeseen, unknown, or unanticipated reactions may occur. Five serious, unexpected serious adverse events have been reported with BMS-986158; 4 of them were assessed to be related to study drug. Two subjects experienced Grade 4 thrombocytopenia, 1 subject experienced Grade 3 vertigo and another subject experienced myocardial infarction. One subject experienced anemia, which was assessed not to be related to BMS-986158.

However, based on the nonclinical safety and toxicity profile of BMS-986158 observed with tested doses in Schedules A, B, and C, the potential safety risks are expected to be minimized, following the planned cautious dose escalation scheme. An urgent need exists for new therapies for subjects with advanced cancer that has progressed or not responded to other treatments. Pharmacologically-active dosing has been achieved at the 4.5 mg dose level in Schedule A. Thus, there may be potential benefits to study subjects with BMS-986158 monotherapy treatment. In addition, based upon potential synergistic effect,²⁵ a combination of BMS-986158 with nivolumab may provide potential additional benefit but will be pursued only after the effects of BMS-986158 on the tumor microenvironment have been characterized. Furthermore, the substantial nonclinical efficacy profile (see Section 1.4.2) and the growing evidence for MYC and BRD4 targeting in many human cancers (see Section 1.1.3), indicates that the balance of benefit to risk is likely to be favorable for study subjects.

This study may allow the characterization of the safety and clinical activity of nivolumab in combination with BMS-986158 depending on the information obtained in the monotherapy dose expansion cohorts and provide an estimate of the clinical benefit as measured by ORR in subjects with advanced cancers associated with genetic abnormalities, including 1) amplifications of BRD, MYC, or AR genes; or 2) mutations in Gnaq/11, KRAS, or SWI/SNF; or 3) translocations of MYC, BCL2/6, or NUT.

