Study Population: The study population will include adult men and women who are at least 18 years of age and adolescents \geq 12 years of age who meet the study eligibility criteria. Adult subjects must have histologic/cytologic confirmation of one of the following malignancies to be eligible: OC, TNBC, NSCLC, RCC, UM, UCS, NEPC, CRPC, NMC, ES, BL, DHL, or non GC-DLBCL. Adolescent subjects must have histologic/cytologic confirmation of NMC, ES, or BL. At least one (1) site of measurable disease as defined by RECIST v1.1 for solid tumors, Lugano 2014 criteria for lymphomas, or PCWG3 for prostate cancers is mandatory. Additionally, in order to be eligible for enrollment to Part 1 of the study, all subjects must have either an archival tumor tissue block or at least twenty (20) unstained cut slides identified and available, and consent to provide this archival tissue. Acquisition of adequate pre-treatment tumor tissue is mandatory for adult subjects in this study. Subjects who do not have archival tissue available may consent to a pre-treatment fresh tumor biopsy to be eligible for this study if it can be performed at acceptable clinical risk as judged by the investigator and if it does not include a target lesion or a lesion in an area treated with prior radiation therapy. All adult subjects enrolled in Part 2 must have tumor lesions that can be biopsied or collected via core needle at acceptable clinical risk (as judged by the investigator) at baseline (pre-treatment), during treatment, and end of treatment (EOT) in case of PD.

Women of childbearing potential (WOCBP) must not be nursing or pregnant and must be using an acceptable method of contraception for at least 4 weeks before dosing and for 5 months following the last dose of study drug. WOCBP must have a negative pregnancy test within 24 hours prior to dosing with study medication. Male participants who are sexually active with a WOCBP should also use an adequate method(s) of contraception, irrespective of vasectomy status or partner's pregnancy status, for up to 7 months following the last dose of study drug.

Revised Protocol No.: 07 Date: 18-Mar-2019

Approved v1000

Study Drug: includes Investigational [Medicinal] Products (IP/IMP) as listed:

BMS-986158 is formulated as a hard gelatin capsule to be administered by oral route.

Nivolumab is formulated as a solution for injection.

Study Drug for BMS-986158

Medication	Potency	IP/Non-IP
BMS- 986158	0.25 mg and 2 mg	IP

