Telemeterized rats demonstrated mild increased heart rate (HR) (~50 bpm) and minimal decreased blood pressure (BP) (~5-10 mmHg) when administered BMS-986158 at 0.5 or 1 mg/kg (AUC[0-24h] \leq 220 ng•h/mL; maximum observed concentration [Cmax] \leq 32 ng/mL).²²⁸ These effects were not dose related. Evaluations of potential BMS-986158-related effects on the cardiovascular nervous, and respiratory systems were conducted as part of the pivotal repeat-dose toxicity studies in rats (nervous, respiratory) and dogs (cardiovascular, nervous, respiratory).^{224,225} There were no clear BMS-986158-related effects on these systems in these studies after 1-month repeat dosing (5 days on/ 2 days off; 20 doses total) at \leq 0.25 mg/kg in rats (AUC \leq 72.2 ng•h/mL; Cmax \leq 13.8 ng/mL) and \leq 0.15 mg/kg in dogs (AUC \leq 106 ng•h/mL; Cmax \leq 19.5 ng/mL).

The potential effects of BMS-986158 on embryo-fetal development were evaluated in an expanded dose range-finding study in pregnant rats.²²⁹ BMS-986158 was administered daily by oral gavage to timed-mated female rats at 0, 0.05, 0.15, or 0.5 mg/kg from Gestation Days (GD) 6 through 16, the period of organogenesis in this species. BMS-986158 was embryolethal at all tested doses. Specifically, there were profound post-implantation losses (manifested mainly as early resorptions) at all tested doses, 63.6% at 0.05 mg/kg/day and 100% at \geq 0.15 mg/kg/day. Additionally, in surviving fetuses at 0.05 mg/kg/day, the mean body weight was reduced (28% less than controls) and malformations (affecting tail, anus, and/or viscera) occurred in 4 of 43 (9.3%) fetuses from 2 of 8 (25%) litters. Based on the results from a previous rat toxicity study,²³⁰maternal AUC values at the lowest observed adverse effect level (LOAEL) of 0.05 mg/kg/day are expected to be 0.002× human exposures following a single dose of 0.75 mg (AUCINF 4.102 µg•h/mL). Increased postimplantation loss has been reported in mouse embryos with BRD2 gene knocked out²³¹ or nullizygous for BRD4.²³²Moreover, in BRD4 heterozygous

mice, prenatal and postnatal growth retardations, malformations of the eyes and bones, and other pathological abnormalities were noted.²³² Therefore, the developmental toxicity observed in litters of BMS-986158-treated dams is consistent with the pharmacological action of BMS-986158.

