- c) All acute toxicities, from any prior therapy (radiotherapy, chemotherapy, or surgical procedures) must have resolved to Grade ≤ 1, NCI CTCAE, version 4.03 or to baseline if irreversible.
- d) Concomitant therapy with bisphosphonates is acceptable as per American Society of Clinical Oncology (ASCO) guidelines. Doses of bisphosphonates must be stable for at least 30 days prior to treatment initiation, as per ASCO guidelines.

4) Age and Reproductive Status

- a) Males and Females, 12 years of age or greater at the time of informed consent.
 - i) For subjects < 18 years of age, age-adjusted normal ranges for all assessments shall be used, as appropriate, for inclusion, exclusion, and dose modification criteria. In addition, an alternate pediatric assessment (eg, left ventricular shortening fraction rather than left ventricular ejection fraction [LVEF]) with an institutionally defined normal range may be used as appropriate.
- b) Women of childbearing potential (WOCBP) must have a negative serum or urine pregnancy test (minimum sensitivity 25 IU/L or equivalent units of HCG) during screening and within 24 hours prior to the start of study drug.
- c) Women must not be breastfeeding
- d) WOCBP must agree to follow instructions for method(s) of contraception for the duration of treatment plus 5 half-lives of study treatments plus 30 days (duration of ovulatory cycle) for a total of 5 months post-treatment completion (see Appendix 11). In addition, female participants must be willing to refrain from donation of oocytes during this time.
- e) Males who are sexually active with WOCBP must agree to follow instructions for method(s) of contraception (Appendix 11) for the duration of treatment with study treatments plus 5 half-lives of study treatments plus 90 days (duration of sperm turnover) for a total of 7 months post-treatment completion. In addition, male participants must be willing to refrain from sperm donation during this time (see Appendix 11).
- f) WOCBP who are continuously not heterosexually active are exempt from contraceptive requirements, and still undergo pregnancy testing as described in this section.

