Investigators shall counsel WOCBP and male subjects who are sexually active with WOCBP on the importance of pregnancy prevention and the implications of an unexpected pregnancy investigators shall advise on the use of highly effective methods of contraception. Highly effective methods of contraception have a failure rate of < 1% when used consistently and correctly.

One of the highly effective methods of contraception listed in Appendix 11 is required during study duration and until the end of relevant systemic exposure, which is defined as 5 months for females and 7 months for males.

Local laws and regulations may require use of alternative and/or additional contraception methods.

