3.3.3 Women of Childbearing Potential

Women of childbearing potential (WOCBP) is defined as any female who has experienced menarche and who has not undergone surgical sterilization (hysterectomy or bilateral oophorectomy) and is not postmenopausal. Menopause is defined as 12 months of amenorrhea in a woman over age 45 in the absence of other biological or physiological causes. In addition, females under the age of 55 years must have a documented serum follicle stimulating hormone, (FSH) level > 40mIU/mL to confirm menopause.

Females treated with hormone replacement therapy, (HRT) are likely to have artificially suppressed FSH levels and may require a washout period in order to obtain a physiologic FSH level. The duration of the washout period is a function of the type of HRT used. The duration of the washout period below are suggested guidelines and the investigators should use their judgement in checking serum FSH levels. If the serum FSH level is >40 mlU/ml at any time during the washout period, the woman can be considered postmenopausal.

- 1 week minimum for vaginal hormonal products, (rings, creams, gels)
- 4 week minimum for transdermal products
- 8 week minimum for oral products

Other parenteral products may require washout periods as long as 6 months.

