APPENDIX 11 WOMEN OF CHILDBEARING POTENTIAL DEFINITIONS AND METHODS OF CONTRACEPTION

DEFINITIONS

Woman of Childbearing Potential (WOCBP)

A woman is considered fertile following menarche and until becoming post-menopausal unless permanently sterile. Permanent sterilization methods include hysterectomy, bilateral salpingectomy, and bilateral oophorectomy.

Women in the following categories are not considered WOCBP

- Premenarchal
- Premenopausal female with 1 of the following:
 - Documented hysterectomy
 - Documented bilateral salpingectomy
 - Documented bilateral oophorectomy

Note: Documentation can come from the site personnel's review of the participant's medical records, medical examination, or medical history interview.

- Postmenopausal female
 - A postmenopausal state is defined as 12 months of amenorrhea in a woman over age 45 years in the absence of other biological or physiological causes. In addition, females under the age of 55 years must have a serum follicle stimulating hormone, (FSH) level > 40 mIU/mL to confirm menopause.

Note: Females treated with hormone replacement therapy, (HRT) are likely to have artificially suppressed FSH levels and may require a washout period in order to obtain a physiologic FSH level. The duration of the washout period is a function of the type of HRT used. The duration of the washout period below are suggested guidelines and the investigators should use their judgement in checking serum FSH levels.

- 1 week minimum for vaginal hormonal products (rings, creams, gels)
- 4 week minimum for transdermal products
- 8 week minimum for oral products

Other parenteral products may require washout periods as long as 6 months. If the serum FSH level is > 40 mIU/ml at any time during the washout period, the woman can be considered postmenopausal.

CONTRACEPTION GUIDANCE FOR FEMALE PARTICIPANTS OF CHILD BEARING POTENTIAL

One of the highly effective methods of contraception listed below is required during study duration and until the end of relevant systemic exposure, defined as 5 months after the end of study treatment.

Local laws and regulations may require use of alternative and/or additional contraception methods.

Highly Effective Contraceptive Methods That Are User Dependent

Failure rate of <1% per year when used consistently and correctly.^a

- Combined (estrogen- and progestogen-containing) hormonal contraception associated with inhibition of ovulation^b
 - oral
 - intravaginal
 - transdermal

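### The protocol gives conflicting contraception rules: 3 months against 5 and 7 months after the last dose, a 4-week lead-in only in the synopsis, and two definitions of childbearing potential.

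*Protocol*

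**What the plan says.** The current Protocol text deals with contraception in several places.

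- Synopsis, Study Population: women of childbearing potential "must be using an acceptable method of contraception for at least 4 weeks before dosing and for 5 months following the last dose". Sexually active men are given a period worded as an upper limit of 7 months.
- Section 1.5, Overall Risk/Benefit Assessment: "Subjects are counseled on appropriate contraceptive measures, while on study and for at least 3 months after the last dose of BMS-986158". The sentence makes no distinction by sex and mentions no lead-in.
- Section 3.3.1, inclusion criterion 4d: "WOCBP must agree to follow instructions for method(s) of contraception for the duration of treatment plus 5 half-lives of study treatments plus 30 days", which the criterion totals as 5 months. Criterion 4e uses 90 days in place of 30 and totals 7 months for men. The closing text of the section repeats the periods: "until the end of relevant systemic exposure, which is defined as 5 months for females and 7 months for males".
- Section 3.3.3: a woman is of childbearing potential if she has reached menarche, "has not undergone surgical sterilization (hysterectomy or bilateral oophorectomy) and is not postmenopausal".
- Appendix 11: "Permanent sterilization methods include hysterectomy, bilateral salpingectomy, and bilateral oophorectomy". It repeats 5 months for women and 7 months for men and has no pre-dose period.

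Section 1.4.2 reports a dose-range-finding study in pregnant rats: "BMS-986158 was embryolethal at all tested doses". The SAP sets no contraception rule.

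**The concern.** Eligibility and counselling ought to rest on one rule. Section 3.3 allows no exceptions to the eligibility requirements, yet the Synopsis contains an entry condition that the criteria themselves do not. Section 1.5 describes to investigators a counselling period whose minimum is below the one subjects must agree to under Section 3.3.1.

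The subject matter raises the stakes. In the rat study, post-implantation loss was 63.6% at the lowest dose and 100% at the higher doses. Maternal exposure at that lowest dose was expected to be 0.002 times human exposure after a single 0.75 mg dose, and Part 2 starts at 4.5 mg, which is 4.5 / 0.75 = 6 times that dose. The trial enrols women, and adolescents from age 12. If sites read different sections, women of childbearing potential could be admitted or counselled differently for no clinical reason.

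**Working it through.** No sample size or error rate is involved. The check sets the statements side by side and measures the differences.

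| Source | Before dosing | After treatment, women | After treatment, men |
|---|---|---|---|
| Synopsis | at least 4 weeks (women) | 5 months | upper limit of 7 months |
| Section 1.5 | not stated | at least 3 months | at least 3 months |
| Section 3.3.1, 4d and 4e | not stated | 5 months | 7 months |
| Section 3.3.1, closing text | not stated | 5 months | 7 months |
| Appendix 11 | not stated | 5 months | 7 months |

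**Post-treatment period.** Women: 5 − 3 = 2 months. Men: 7 − 3 = 4 months. At 30.4375 days per month (the conversion in SAP Section 8.1), these are 2 × 30.4375 = 60.9 days and 4 × 30.4375 = 121.75 days. Section 1.5 is the only outlier on length. The Synopsis wording for men agrees on the figure but makes it a ceiling, where Section 3.3.1 and Appendix 11 make it a fixed period.

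**Lead-in.** Take a woman with negative pregnancy tests who starts a qualifying method the day before first dose and agrees to continue it for 5 months afterwards. She satisfies the contraception terms of Section 3.3.1 and Appendix 11. She fails the Synopsis condition, because 1 day is less than 28. The texts therefore give different answers on eligibility and on the earliest dosing date.

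**Definition.** Take a premenopausal woman with bilateral salpingectomy and no other procedure. Section 3.3.3 names hysterectomy and bilateral oophorectomy only, so she counts as of childbearing potential and owes pregnancy tests and contraception. Appendix 11 adds salpingectomy, so she does not count and owes neither. Section 3.3.3 is the more inclusive of the two. The women affected are those Appendix 11 treats as permanently sterile, so the mismatch changes obligations and leaves nobody less protected.

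**The half-life formula, checked because it might explain the gap.** Section 1.1.5 gives a human half-life of 39 hours for BMS-986158.
- 5 × 39 h = 195 h = 8.1 days.
- Women: 8.1 + 30 = 38.1 days. Men: 8.1 + 90 = 98.1 days.
- Working back from the stated totals: 5 months = 152.2 days and (152.2 − 30) / 5 = 24.4 days; 7 months = 213.1 days and (213.1 − 90) / 5 = 24.6 days.

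Both totals imply nearly the same half-life, far longer than 39 hours. Nivolumab is the other study treatment, but the documents give no half-life for it, so the totals can be neither reproduced nor refuted.

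**The case against.** The best reply is that the operative text is consistent. The Synopsis, the inclusion criteria and Appendix 11 all carry 5 and 7 months, and criteria 4d and 4e point to Appendix 11. Section 1.5 is a single descriptive sentence in a background section, and its minimum is met by anyone who follows 5 or 7 months. It also refers to BMS-986158 alone, whereas the criteria refer to study treatments in the plural, so part of the gap may reflect different drugs. The lead-in conflict is a requirement against silence, not against a contrary rule, and criterion 4b separately requires negative pregnancy tests at screening and within 24 hours before dosing. The consent form is not among the documents, so what subjects are actually told cannot be judged.

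Most of this stands and limits the weight of the point. It does not remove it. A stated minimum of 3 months still permits counselling shorter than the eligibility text, and criteria 4d and 4e give no separate monotherapy period. Silence in criteria that allow no exceptions still yields a different eligibility decision from the Synopsis.

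Four stronger readings are tempting, and the documents do not support them.

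- *That the Synopsis sets a weaker method standard.* It asks women for an acceptable method, while Section 3.3.1 requires a highly effective one. Appendix 11, however, lists the less effective methods as not acceptable for participants, so the Synopsis term can be read consistently with it.
- *That the half-life derivation is wrong.* The 39-hour figure covers one agent. Without a nivolumab half-life the formula cannot be tested.
- *That protection at a site turns wholly on which section it reads.* The operative sections agree on duration.
- *That the embryolethality finding supports the male period.* It comes from dosed pregnant rats and says nothing direct about men.

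**Conclusion.** Wrong as written: the Protocol contradicts itself in current text on three matters.

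1. The post-treatment minimum in Section 1.5 is 2 months shorter for women and 4 months shorter for men than the periods in the eligibility text and Appendix 11.
2. The 4-week lead-in appears only in the Synopsis, so eligibility and the earliest dosing date depend on the text applied.
3. Bilateral salpingectomy is classified in two ways, which affects testing and contraception obligations but opens no gap in protection.

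The second matter has the most direct operational effect, because it decides who may be dosed and when. The first affects counselling. The third is minor. The conclusion rests on a comparison of wording and does not depend on any assumed half-life. It does not say which duration, lead-in or definition is right. No endpoint, sample size or analysis is affected.

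**What to change.** Reconcile the Synopsis, Section 1.5, Section 3.3.1 (criteria 4d and 4e and the closing text), Section 3.3.3 and Appendix 11 to one statement on the lead-in, including whether there is one; one post-treatment duration per sex, with the male period worded the same way throughout; and one definition of childbearing potential. Hold the rule in one place and replace the other statements with cross-references. Check the consent form against the result. The sponsor decides the values.

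The cost is protocol wording and a consent-form check. If a lead-in is kept, some women may wait longer for first dose. A 4-week lead-in takes 28 days, which leaves 40 − 28 = 12 days of the Part 2 screening window but none of the 28-day Part 1 window, assuming the method starts on the first day of screening.
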